## 7. What tests will be done and how often

No tests will be done. Survey data will be collected at baseline, 3 months, 6 months and 12 months.

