## 8. What information will be collected

From baseline to 3 months, to 6 months, and to 12 months, we will measure change in:

- a. **Frequency of opioid use.** We will assess frequency of opioid use in the past three months from 1 = never to 6 = over 20 times.
- b. **Frequency of alcohol and cannabis use.** We will assess frequency of opioid use in the past three months from 1 = never to 6 = over 20 times.
- c. **Social Network Composition.** Participants will be asked to name 15 contacts (“alters”) who are at least 18 years of age. Participants will rate each of the 15 people on the same set of questions with categorical response options (about demographics, relationship quality, likelihood to use drugs, etc.). For each participant the selected responses will be summed across all the network alters and divided by 15 to produce network composition percentages of the whole set of alters named by the participant (% of AI/ANs, % who engage in heavy drinking).
- d. **Cultural connection.** Cultural connection will be measured with 29 items that address 3 dimensions: identity, traditions, and spirituality. Respondents answer 11 yes/no questions (e.g., I have a traditional person, Elder, or other person who I talk to), and use a scale from 1= “strongly disagree” to 5= “strongly agree” for 18 items (e.g., I feel a strong connection/attachment towards my Native American community or Tribe). We will also measure this via participation in 26 different types of traditional practices (e.g., going to Pow Wows, beading, traditional dancing). Items were based upon extensive research conducted with AIAN young people, parents, and community partners.
- e. **Social Network Structure.** Participants will rate the relationship strength between each of the 15 named alters. For each alter pair they will rate if the two people know each other and, if yes, have they connected recently. Measures of network structure (i.e. network “connectedness”) will be constructed from the set of evaluations for each participant. For example, network “density” will be constructed for the network overall, which is calculated by summing the number of alter pairs who know each other and dividing by the total number of possible ties among 15 alters (105). Individual alter “centrality” will be calculated by summing the number of connections each individual alter has with other alters in the network.

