## 1. Statistical aspects of the clinical trial design

**Aim 2.** We will compare outcomes at 3-, 6- and 12-months for AI/AN EAs who receive opioid education (n=185) to AI/AN EAs who receive TACUNA+WC (n=185).

**Aim 3.** We will conduct mediation analyses to examine whether changes in social networks and cultural connectedness serve as explanatory mechanisms for reductions in opioid and AOD use.

**Aim 4. Sustainability.** We will develop and test strategies to facilitate sustainability of TACUNA within these communities through 20 key informant interviews.

**Aim 5. Economic evaluation.** We will follow recommendations from the Panel of Cost-Effectiveness in Health and Medicine, by reporting costs and cost-effectiveness estimates in terms of two reference cases, one based on a program perspective (programmatic and provider time costs) and the other on a societal perspective that incorporates a broader range of costs, such as opportunity costs to participants.

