## 4. Procedures and methods employed for analyzing the data

### Aim 2

*Analysis.* Our analytic approach will focus on use and consequences, cognitions, social networks, and cultural connection outcomes. We will compare opioid education participants to TACUNA+WC participants, with covariates age, gender, and the baseline measure of the outcome of interest. Given the longitudinal design, we may implement more than one analytic method to address this aim. One option is to use a multigroup latent growth model framework using robust maximum likelihood for continuous outcomes or weighted least square mean and variance for categorical outcomes. Alternatively, we may use SAS Proc Mixed will be used for continuous outcomes and SAS Proc Glimmix/NLMixed for categorical outcomes. In addition to examining overall longitudinal trends across the entire study, we will also examine outcomes at each timepoint (3, 6, and 12 month) using multivariable linear regression for normally distributed outcomes and multivariable logistic regression for dichotomous outcomes, controlling for the baseline value of the outcome and participant demographics (age, sex, and sexual and gender diverse identity). The estimated adjusted difference between intervention groups at follow-up (or odds ratio for dichotomous outcomes) and the corresponding 95% confidence interval (CI) will be presented, along with the p-value and Cohen's effect size. Evaluating differences at each timepoint provides estimates of the intervention effect at a given timepoint whereas the longitudinal methods will address patterns of change over the course of the intervention. To enhance interpretability of our results, we will use estimated differences between groups to calculate standardized effect sizes in terms of  $d$  (for continuous variables, using the standard deviation of the opioid education only group as denominator); we will use odds ratio estimates to calculate risk difference and number needed to treat, based on outcome proportions for the opioid education group.

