*Power.* The N of 370 was determined in a priori power analyses to be sufficient to detect small to moderate intervention effect sizes for all primary and secondary outcomes. We chose to use the final projected sample size accounting for 20% attrition at the 12-month follow up (n=148 per arm). Within a repeated measures framework, these sample sizes, assuming a correlation between repeated assessments of 0.50, four timepoints, and alpha of .05, we have 80% power to detect a standardized effect size ( $d$ ) of 0.31 between groups and .22 within groups. For mediation models, using bias-corrected bootstrapping, there is 80% power to detect a mediated/indirect effect when  $\delta=0.28$  (i.e., effect of the predictor on the mediator) and  $\beta=0.26$  (i.e., effect of the mediator on the outcome).

### Aim 3

Mediation models will be used to determine whether changes in cultural connectedness and social networks serve as mechanisms for reducing opioid, cannabis, and alcohol use. First we will test multivariate mediation to determine if the total mediation effect is statistically significant to control Type I error rate. If the total mediated effect is significant, we will then examine individual mediators to determine statistical significance. The estimate of the effect of the intervention on the outcome can be divided into the direct effect and the indirect (mediated) effect. The standard errors of the individual indirect effects will be estimated using bias-corrected bootstrapping. For mediation models, using bias-corrected bootstrapping, with these projected sample sizes, there is 80% power to detect a mediated/indirect effect when  $\delta=0.28$  (i.e., effect of the predictor on the mediator) and  $\beta=0.26$  (i.e., effect of the mediator on the outcome). Results will provide information about efficacy for each intervention. Results can improve the design of future studies by providing information such as intra-class correlations within groups, which will allow researchers to estimate sample sizes and effect sizes for power analysis.

## Aim 5

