*Costs.* We will account for programmatic costs following the micro-costing approach of prior work. Intervention costs will be obtained from several sources, including program records and primary collection of cost and time use data. Programmatic input costs include labor (including overhead), materials, and other costs of implementing the intervention; for the societal perspective, we will also consider (a) transportation costs to participants; (b) opportunity costs of EAs; and (c) space and utility costs. The analysis will exclude research costs, although we can incorporate these in sensitivity analyses.

*Effectiveness.* We will follow recommendations for economic evaluations of AOD use interventions and consider multiple outcomes from Aim 2 analyses to compare effectiveness at 6 and 12 months after baseline. Our primary effectiveness measures will be abstention from opioid misuse in the past 3 months (either through preventing initiation or discontinuing use); abstention or consumption below the threshold of heavy use for alcohol and cannabis; and a reduction in time spent around peers who misuse opioids. Given our focus on prevention, an effectiveness outcome related to peers will be informative.

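### Adding the six-category baseline frequency score to the visit-specific logistic models would give a modest, cheap gain in power for alcohol- and cannabis-type yes/no outcomes, provided risk differences are standardised

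*Combined protocol and SAP*

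**What the plan says.** The general Aim 2 comparison (SAP section 4) is to be made "with covariates age, gender, and the baseline measure of the outcome of interest". For the separate analyses at 3, 6 and 12 months, the same paragraph plans "multivariable logistic regression for dichotomous outcomes, controlling for the baseline value of the outcome and participant demographics"; the demographics are age, sex, and sexual and gender diverse identity. It then converts odds ratios to risk differences and numbers needed to treat, using the outcome proportions of the opioid education group.

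Protocol section 8 (item a) scores opioid use "in the past three months from 1 = never to 6 = over 20 times". Item b, headed alcohol and cannabis, repeats the opioid wording: "Frequency of alcohol and cannabis use. We will assess frequency of opioid use in the past three months from 1 = never to 6". The scores exist before treatment, since protocol section 7 states "Survey data will be collected at baseline, 3 months, 6 months and 12 months".

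The only yes/no measure for alcohol or cannabis is in the Aim 5 Effectiveness paragraph of SAP section 4: "abstention or consumption below the threshold of heavy use for alcohol and cannabis". It is drawn from Aim 2, but neither the threshold nor the source item is given.

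**The concern.** The baseline value of a yes/no outcome is, on its face, itself yes/no. With any use as the outcome, a participant who used rarely and one who used more than 20 times in three months then carry the same covariate value. The six-category score separates them and should predict follow-up status better.

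In a logistic model a stronger baseline predictor increases power for the arm effect while leaving type I error alone. At stake is some precision in the visit-specific tests of yes/no outcomes, and in any Aim 5 measure derived from the same items. If the finer score was intended all along, the SAP should say so, so that the form of the covariate is fixed before results are seen.

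**Working it through.** **Inputs from the documents.** SAP section 1 compares those "who receive opioid education (n=185) to AI/AN EAs who receive TACUNA+WC (n=185"). The Power paragraph of SAP section 4 works with the final sample, "accounting for 20% attrition at the 12-month follow up (n=148 per arm"); 185 × 0.8 = 148. It assumes correlation 0.50, four timepoints and alpha .05 (two-sided assumed here), and states 80% power for d = 0.31 between groups and 0.22 within groups. It gives no power figure for a dichotomous outcome.

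**The plan's own figure.** It is reproduced by a linear trend over four equally spaced timepoints with compound symmetry:

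- SD of (slope × study length) = √(9 × 0.5 / 5) = 0.949.
- Between groups: Φ(0.31 / (0.949 × √(2/148)) − 1.96) = Φ(2.81 − 1.96) = 80.3%.
- Within groups: Φ(0.22 × √148 / 0.949 − 1.96) = Φ(2.82 − 1.96) = 80.5%.

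This is a calculation for a continuous outcome, so the choice of covariate in the logistic models does not touch it.

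**Power simulation.** The documents do not give the following, so they are assumed:

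- Latent normal baseline and follow-up use, cut into six categories.
- Category shares of 35/20/15/10/8/12% (alcohol-like) and 50/12/8/6/4/20% (cannabis-like).
- Outcome defined as any use (category 2 and above) or category 4 and above.
- Latent arm shift set so that the model with the yes/no baseline has about 80% power.

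There were 148 per arm and 6,000 trials per setting. The last column is ((1.96 + z of power with both) / (1.96 + z of power with yes/no))². For the first row: ((1.96 + 1.028) / (1.96 + 0.946))² = 1.057.

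| Outcome | Score correlation | Shift | Unadjusted | Yes/no baseline | Yes/no + score | Gain (points) | Equivalent N |
|---|---|---|---|---|---|---|---|
| Alcohol-like, any use | 0.49 | 0.40 | 78.9% | 82.8% | 84.8% | 2.0 | 1.057 |
| | 0.64 | 0.37 | 70.5% | 81.1% | 84.0% | 2.9 | 1.081 |
| | 0.74 | 0.34 | 64.4% | 80.4% | 84.1% | 3.7 | 1.104 |
| Alcohol-like, category 4+ | 0.49 | 0.44 | 77.1% | 81.6% | 83.6% | 2.0 | 1.055 |
| | 0.64 | 0.40 | 69.5% | 78.9% | 82.4% | 3.5 | 1.095 |
| | 0.74 | 0.37 | 63.2% | 78.2% | 84.2% | 6.0 | 1.170 |
| Cannabis-like, any use | 0.44 | 0.40 | 78.1% | 83.0% | 84.6% | 1.6 | 1.045 |
| | 0.59 | 0.37 | 71.3% | 81.5% | 84.1% | 2.6 | 1.073 |
| | 0.70 | 0.34 | 64.8% | 81.0% | 84.8% | 3.8 | 1.109 |
| Cannabis-like, category 4+ | 0.44 | 0.44 | 76.0% | 80.3% | 81.9% | 1.6 | 1.043 |
| | 0.59 | 0.40 | 71.0% | 79.9% | 82.9% | 3.0 | 1.082 |
| | 0.70 | 0.37 | 63.8% | 79.1% | 83.0% | 3.9 | 1.107 |

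Other settings agree. With 50% or 70% users, any use, a shift of 0.35 and 4,000 trials, power rose from 70.7% to 71.6% and from 69.4% to 71.3% at latent correlation 0.5 (score correlation 0.41 to 0.44). At latent correlation near 0.57, which gives a score correlation of about 0.50, the gains were 1.5 and about 3 points. For an opioid-like outcome (8% any use, shift 0.31) the change was −0.1 to +0.4 points. Type I error was 4.8 to 4.9% in the null run.

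**Effect on the risk difference.** One million simulated participants, 50% users, shift 0.35, any use, demographics omitted. The converted columns apply the model's odds ratio to the control proportion, as the SAP plans.

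| Latent correlation | True risk difference | Converted, yes/no baseline | Converted, yes/no + score |
|---|---|---|---|
| 0.5 | −13.6 | −15.2 | −15.6 |
| 0.7 | −13.8 | −17.7 | −19.0 |
| 0.85 | −13.7 | −22.1 | −25.0 |

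At 0.85 the number needed to treat is 1/0.137 = 7.3 in truth, 1/0.221 = 4.5 as planned and 1/0.250 = 4.0 with the score added. Averaging model predictions under each arm recovers about −14 points.

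**The case against.** A reader might infer that the SAP adjusts for the yes/no baseline and nothing else, or that it rules the frequency score out. It does neither. The same sentence adds demographics, the general Aim 2 sentence refers more loosely to a baseline measure, and the form of the covariate is never specified. The yes/no reading is the literal one, no more.

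A reader might also infer a material loss of power on named alcohol and cannabis outcomes. Aim 2 names no yes/no outcome for either substance. Where the 1 to 6 score is itself the outcome, its baseline value is already the six-category score. The Aim 5 measure has no stated threshold and feeds cost-effectiveness ratios with bootstrap intervals, so precision is the relevant loss there. Item b of protocol section 8, as worded, does not even confirm that the item is asked for alcohol and cannabis, although its heading makes a copying slip likely. Opioid misuse, the trial's focus, gains almost nothing. All of this stands.

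Two objections bear on the remedy. Odds ratios are non-collapsible, so adding the score without changing the risk-difference step would enlarge an existing distortion. And the Power paragraph counts four timepoints, so baseline may be a repeated response in the longitudinal models; adding it there as a covariate would use it twice, and the simulations covered single-visit models only. Both stand and limit the fix.

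**Conclusion.** The point holds as a cheap improvement, not as an error. The planned logistic adjustment is valid, and most of the benefit of baseline adjustment already comes from the yes/no value: in the first row of the power table it adds 82.8 − 78.9 = 3.9 points, and the score a further 2.0.

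For yes/no outcomes derived from a common-use frequency item, the gain is about 1.5 to 2.5 points near the SAP's correlation of 0.50 (individual settings from about 1 to 3), equivalent to roughly 4 to 6% more participants. It is about 3 to 5 points if use is more stable than the SAP assumes, with 6.0 in the most favourable setting. For rare opioid use it is close to zero. These sizes rest on assumed category distributions, cutpoints, arm shifts and a latent normal model, and the higher correlations have no support in the documents.

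**What to change.** - In SAP section 4, Aim 2 Analysis, state that the visit-specific logistic models for yes/no outcomes derived from a frequency item adjust for the baseline six-category score of the same substance together with the baseline yes/no value, in addition to the listed demographics.
- In the same paragraph, compute risk difference and number needed to treat by averaging model predictions under each arm, instead of applying the conditional odds ratio to the control proportion.
- Use those standardised estimates for any Aim 5 measure derived from a frequency item.
- Correct item b of protocol section 8 so that it confirms the item is asked for alcohol and for cannabis.
- Do not add the score to longitudinal models in which baseline is already a repeated response.

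The cost is one extra model term and a standardisation step. No new data are needed, provided the item is asked for both substances.

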## 3. Detailed analyses of data items

*Descriptives.* We will examine descriptive statistics and examine missing data. Frequencies will be evaluated for evidence of sparseness for categorical data and for non-normality (using plots, examination of skewness, kurtosis, etc.) for continuous variables. If sparseness is present for categorical variables, we will collapse as necessary to produce cell sizes sufficient for analysis. Where non-normality is evident, variables may be transformed. Outliers may be recoded or omitted if necessary. Missing data will be dealt with using multiple imputation and/or full information maximum likelihood estimation. All outcomes will be presented using descriptive statistics; continuous variables by the mean and standard deviation (SD), and dichotomous variables by the number and percentage. Descriptive statistics will be provided at both baseline and follow-up.

*Baseline equivalence across experimental groups.* We will evaluate comparability of experimental groups with respect to potential confounders. Categorical methods of analysis (e.g. cross tabulations, chi-square) will be used to compare groups for discrete data (e.g., employment, school status). ANOVA or t-tests will be used to test for homogeneity of groups for continuous data at baseline. If a statistically significant difference is found, the covariates will be included in all subsequent analyses.

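### Risk difference and NNT obtained by applying a covariate-adjusted odds ratio to the control arm's overall risk will overstate the absolute effect

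*Combined protocol and SAP*

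**What the plan says.** SAP section 4 (Aim 2, Analysis) plans, at each timepoint, "multivariable logistic regression for dichotomous outcomes, controlling for the baseline value of the outcome and participant demographics", the demographics being age, sex, and sexual and gender diverse identity. The overall comparison is made "with covariates age, gender, and the baseline measure of the outcome of interest". For longitudinal work one option is "SAS Proc Glimmix/NLMixed for categorical outcomes", with the random-effects structure not stated. SAP section 3 can add further covariates: "If a statistically significant difference is found, the covariates will be included in all subsequent analyses".

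As an aid to interpretation, section 4 then converts to absolute measures: "we will use odds ratio estimates to calculate risk difference and number needed to treat, based on outcome proportions for the opioid education group".

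The plan does not say whether those proportions are observed or model-based. The only proportions it defines are the descriptive ones in SAP section 3, which summarises "dichotomous variables by the number and percentage". No unadjusted odds ratio and no averaging of predicted risks over the covariates appears anywhere.

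**The concern.** The conversion joins two quantities that refer to different things. The odds ratio is conditional: it compares arms among people with the same baseline value and demographics. The control proportion is marginal: it is the risk over the whole arm. Even under perfect randomisation, if a covariate predicts the outcome and there is an effect, the conditional odds ratio lies further from 1 than the marginal one. Applying it to the marginal control risk therefore gives a TACUNA+WC risk that is too far from the control risk. An odds ratio from a model with random effects is subject-specific and raises the same problem.

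Risk difference and NNT are the figures readers will use to judge practical benefit, and the error does not shrink with more participants. Prior use is a natural predictor of later use. The dichotomous effectiveness measures that Aim 5 takes from Aim 2 (abstaining from opioid misuse; abstaining from, or staying below heavy use of, alcohol and cannabis) are outcomes of that kind.

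**Working it through.** The documents state no risk difference, NNT, odds ratio or control proportion, so there is no planned figure to reproduce. All inputs below are assumptions, except 148 per arm (SAP section 4, Power: 185 × 0.8 = 148).

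**Formulas.** Let B be baseline use, q = P(B=1), and r₁, r₀ the control-arm follow-up risks in baseline users and non-users.
- Control risk: p₀ = q·r₁ + (1−q)·r₀.
- True TACUNA+WC risk p₁: apply the conditional odds ratio to the odds within each stratum, convert back to risks, and average with weights q and 1−q.
- Plan's formula: odds(p*) = OR × odds(p₀).
- Compare p₁ − p₀ with p* − p₀. NNT is the reciprocal of the absolute difference.

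**One case by hand.** Take q = 0.20, r₁ = 5/9, r₀ = 1/9, conditional OR 0.5.
1. p₀ = 0.20 × 0.5556 + 0.80 × 0.1111 = 0.200. The baseline-to-follow-up odds ratio is (5/4)/(1/8) = 10.
2. Users: odds 1.25 become 0.625, risk 0.3846. Non-users: odds 0.125 become 0.0625, risk 0.0588.
3. p₁ = 0.20 × 0.3846 + 0.80 × 0.0588 = 0.1240. True risk difference −0.0760, NNT 13.2.
4. Plan's formula: odds 0.25 become 0.125, risk 0.1111. Risk difference −0.0889, NNT 11.3.
5. Overstatement: 0.0889/0.0760 = 1.17, or 17%.

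**Range.** Overstatement of the risk difference, conditional OR 0.5, q set equal to p₀:

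| Control risk | Baseline OR 3 | Baseline OR 10 | Baseline OR 20 | NNT at baseline OR 10, true / formula |
|---|---|---|---|---|
| 5% | 0.4% | 3.7% | 9.2% | 42.6 / 41.1 |
| 20% | 2.8% | 17% | 33% | 13.2 / 11.3 |
| 30% | 4.5% | 24% | 45% | 10.0 / 8.1 |
| 50% | 6.9% | 33% | 60% | 8.0 / 6.0 |

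With a non-prognostic covariate (baseline OR 1) the two calculations agree exactly.

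**Against sampling error.** The crude standard error is √[p₀(1−p₀)/148 + p₁(1−p₁)/148]. At p₀ = 0.30 and baseline OR 10, p₁ = 0.2002 and the standard error is 0.0500. The bias is 0.1235 − 0.0998 = 0.0237, or 0.47 standard errors. The corresponding values are 0.04 at 5% control risk and 0.72 at 50%.

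**Harm.** Take q = 0.30, r₁ = 0.60, r₀ = 0.08 (baseline OR 17), conditional OR 2.0. Then p₀ = 0.236 and p₁ = 0.30 × 0.750 + 0.70 × 0.148 = 0.329, a true difference of +9.3 points. The formula gives odds 0.309 × 2 = 0.618, risk 0.382, a difference of +14.6 points.

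**Random intercepts.** With a subject-specific OR of 0.5 and intercept SD 1 to 3, the formula overstates the risk difference by a factor of 1.06 to 1.56 at 10% control risk and 1.19 to 2.11 at 50%.

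**Simulation** (148 per arm, logistic model on arm and baseline use; 2,000 trials for the first three rows, 1,500 for the last). Risk differences are in points, mean (SD):

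| Scenario | True | Plan's formula | Standardised |
|---|---|---|---|
| 30% users, risks 60% and 8%, OR 0.5 | −7.8 | −10.1 (5.0) | −7.8 (4.0) |
| Same, OR 2.0 | +9.3 | +15.0 (7.3) | +9.3 (4.3) |
| Control risk 30%, 30% users, baseline OR 3, OR 0.5 | −11.8 | −12.5 (5.1) | −12.0 (4.9) |
| Control risk 30%, 30% users, baseline OR 10, no effect | 0 | 0.0 (6.4) | −0.1 (4.8) |

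Standardisation removes essentially all the bias and is less variable in every row.

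**The case against.** **The reading is an inference.** The sentence says neither adjusted nor observed, and gives no formula. True, but every odds ratio model in section 4 is adjusted. If model-based averaging is what the sponsor intends, that is the remedy proposed here and the SAP need only say so.

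**The bias is relative to a marginal target that the plan never names.** An odds ratio applied to a reference risk is a valid risk difference for a person whose own control risk has that value. This carries little weight, because a group's outcome proportion is most naturally a population risk.

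**Reach may be narrow.** Use is collected on a 1-to-6 frequency scale, and section 4 names no specific dichotomous outcome. If initiation were analysed only among baseline non-users, baseline use would be constant and the main driver would go. Opioid misuse may also be uncommon in a prevention trial that excludes opioid use disorder, and at 5% control risk the absolute error is at most 0.21 points over the baseline odds ratios tabulated. These limits stand. The sentence is not confined to opioids, however, and the alcohol and cannabis measures may be much commoner, which is itself an assumption.

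**The larger figures need strong assumptions.** The 45% and 60% entries need a baseline odds ratio of 20 with control risk of 30% to 50%. With a conditional odds ratio of 0.7 and baseline odds ratio 10, the bias falls to 0.29 standard errors at 30% risk and 0.40 at 50%, although the relative overstatement rises slightly, to 28% and 36%. This limits the size and leaves the direction unchanged. Letting the odds ratio differ between baseline users and non-users did not reverse the direction in any scenario tried.

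**Conclusion.** The concern holds. Followed as written, the conversion overstates the absolute effect in whichever direction it runs. The large-sample bias is zero if there is no effect or the covariates are not prognostic, so it exaggerates an effect and does not create one. It is negligible for rare outcomes with weak predictors. It is material, about 17% to 33% of the risk difference, for control risks of 20% to 50% with a baseline-to-follow-up odds ratio of 10 and a conditional odds ratio of 0.5, and larger with stronger predictors. Those inputs are assumed.

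The odds ratio, its confidence interval, the hypothesis test and the power statement are untouched. The cost-effectiveness ratios are affected only if they use this risk difference, which the Aim 5 text does not state. This is a fault in a reported measure that should be corrected; it does not threaten the primary inference.

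**What to change.** Replace the conversion sentence in SAP section 4 with marginal standardisation, for example:

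> For each dichotomous outcome and timepoint, each randomised participant's predicted risk under TACUNA+WC and under opioid education will be computed from the fitted logistic model and averaged over all randomised participants. The difference between the two averages is the risk difference and its reciprocal the NNT, with delta-method or bootstrap 95% confidence intervals.

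Three additions complete it:
- With multiple imputation, do this within each imputed data set and pool.
- With a random-effects model, integrate the predictions over the random effect.
- Use this risk difference wherever an Aim 2 risk difference enters a cost-effectiveness ratio.

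The cost is one SAP sentence and a few lines of code. Design, data collection and hypothesis tests do not change. The reported absolute effect will be somewhat smaller, in either direction, than the present formula would give.
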